## 8.2 Randomization

Eligible subjects will be randomized into either one of three M2951 groups [REDACTED] or the placebo group in a ratio of 1:1:1:1, stratified according to race (Black versus non-Black), region (US and Western Europe, Japan, and RoW) and Screening disease activity (SLEDAI-2K total score  $< 10$  versus  $\geq 10$  at Screening). A randomized allocation schedule for IMP assignment will be generated within the appropriate group of [REDACTED], by an individual who is not on the study team. Randomization will occur using the IWRS as described in Section 6.3 upon completion of the Screening/Baseline procedures and determination of subject eligibility.

To ensure enrollment of an adequate number of subjects with HDA, recruitment of subjects without HDA may be capped, depending on enrollment rates observed during the study of subjects with and without HDA.

## 8.3 Endpoints

### 8.3.1 Primary Endpoints of Efficacy and Safety

The co-primary efficacy endpoints are SRI response at Week 52: SRI-4 in all subjects and SRI-6 in a HDA subgroup. The SRI-4 response, a measure of reduced SLE disease activity, is defined by meeting all of the following conditions compared to Baseline:

1.  $\geq 4$  point reduction in SLEDAI-2K total score.
2. No significant worsening in PGA score ( $< 0.3$  increase assuming the PGA score is on a 0-3 scale).

3. No new BILAG A organ domain scores and  $\leq 1$  new BILAG B organ domain score compared to Day 1 using BILAG 2004.
4. No discontinuation of investigational product and no institution of protocol-prohibited medication/treatment

The SRI-6 response is defined similarly to SRI-4, based on a  $\geq 6$  point reduction in SLEDAI-2K total score. For SRI response, Baseline is defined as Day 1 predose.

In this study, safety endpoints are considered to be primary endpoints. The safety endpoints are:

- Nature, severity, and incidence of AEs, SAEs, vital signs, ECGs, absolute values and change from Baseline in serum total Ig levels (IgG, IgA, IgM) and total B cell counts, and clinical laboratory parameters.

### 8.3.2 Secondary Endpoints

The key secondary endpoints are:

- Time to first severe flare, where a severe flare is defined as at least one BILAG A score in any organ system due to items that are new or worse, compared to the BILAG evaluation at the previous visit, during the Treatment Period
- SRI-4 response at Week 52, in the serologically active subgroup, which is defined as subjects with positive anti-dsDNA and/or low complement levels.

Other Secondary endpoints are:

- SRI-6 response at Week 52, in the serologically active subgroup, which is defined as subjects with positive anti-dsDNA and/or low complement levels.
- SRI-4 Response at Week 52 with a Sustained Reduction of OCS Dose to 7.5 milligrams prednisone-equivalent per day or less ( $\leq 7.5$  mg/day) and less than or equal to ( $\leq$ ) Day 1 dose during Week 41 Through Week 52, in all subjects.
- SRI-6 Response at Week 52 with a Sustained Reduction of OCS Dose to 7.5 milligrams prednisone-equivalent per day or less ( $\leq 7.5$  mg/day) and less than or equal to ( $\leq$ ) Day 1 dose during Week 41 Through Week 52, in the HDA subgroup, defined as SLEDAI-2K  $\geq 10$  at Screening.
- SRI-4 Response at Week 52 with a Sustained Reduction of OCS Dose to 7.5 milligrams prednisone-equivalent per day or less ( $\leq 7.5$  mg/day) and less than or equal to ( $\leq$ ) Day 1 dose during Week 41 Through Week 52, in the serologically active subgroup, which is defined as subjects with positive anti-dsDNA and/or low complement levels.
- Time to first flare, flare-free status at Week 52, and annualized flare rate, during the Treatment Period, will be analyzed separately, each assessed with flare defined as:
  - BILAG A Severe flare
  - BILAG A or 2B Moderate to Severe flare

- SFI Severe flare
- Disease activity over time, during the Treatment Period, as measured by:
  - Low disease activity status, defined by SLEDAI-2K  $\leq 2$ , at Week 52
  - Low disease activity status, defined by clinical SLEDAI-2K (SLEDAI 2K excluding anti-dsDNA and low complement parameters)  $\leq 2$ , at Week 52
  - Lupus low disease activity state (LLDAS), defined as meeting all of the following (Franklyn 2016):
    - SLEDAI-2K  $\leq 4$
    - No activity in any major organ systems (renal, central nervous system, cardiopulmonary, vasculitis, fever)
    - No new features of disease activity compared with the previous assessment
    - Prednisone-equivalent  $\leq 7.5$  mg/day
    - Unchanged background immunosuppressive therapy
  - Change from Baseline in SLEDAI-2K score by visit
  - Change from Baseline in CLASI-A by visit
  - BICLA response by visit
  - Change from Baseline in BILAG-2004 by visit
  - Change from Baseline in PGA by visit
- HRQoL over time, during the Treatment Period, as measured by:
  - Change from Baseline in SF-36v2 PCS and MCS scores (and their components) by visit
  - Change from Baseline in EQ-5D-5L score by visit
  - Change from Baseline in LupusQoL score by visit
  - PGIC score by visit
  - Change from Baseline FACIT-Fatigue score by visit
- Corticosteroid usage over time, during the Treatment Period, as measured by:
  - Reduction from Baseline in prednisone-equivalent CS dose by  $\geq 25\%$  to a dose of  $\leq 7.5$  mg/day, with no BILAG A or 2B flare in disease activity (at that visit)
  - Change from Baseline to Week 52 in prednisone-equivalent CS daily dose
  - Reduction from Baseline to Week 52 in prednisone-equivalent CS daily dose of zero to  $< 25\%$ ,  $25\%$  to  $50\%$ ,  $> 50\%$ , or an increase
  - Cumulative prednisone-equivalent CS dose from Baseline until completion of the Treatment Period
  - Clinically meaningful reduction in CS dose from Baseline, defined by:

- A reduction of daily prednisone-equivalent CS dose  $\geq 25\%$  to a dose of  $\leq 7.5$  mg/day by Week 40 and sustained through Week 52

AND

- No new BILAG A organ domain scores and no more than one new BILAG B organ domain score during Weeks 40 through 52.

### **8.3.3 Exploratory Endpoints**

Exploratory endpoints are:

CCI

### 8.3.4 Endpoints for Long-Term Extension Period

#### LTE Safety:

- Nature, severity, and incidence of AEs, SAEs, vital signs, ECGs, absolute values and change from Baseline in serum total Ig levels (IgG, IgA, IgM) and total B cell counts, and clinical laboratory parameters.

#### LTE Efficacy:

- The following LTE efficacy endpoints will be analyzed at Week 24, Week 52, and Week 104:
  - Changes over time in SRI response
  - Changes over time in Low Disease Activity status (LLDAS, SLEDAI-2K $\leq$ 2, clinical SLEDAI-2K $\leq$ 2).
  - Changes over time in CLASI-A, CLASI-D, and SLICC/ACR Damage Index organ damage scores
  - Changes over time in disease activity as measured by the BILAG, SLEDAI-2K, and PGA
  - Change over time in prednisone-equivalent CS dose
  - Changes over time in HRQoL
  - Changes over time in autoantibodies and complement levels
- Changes in HRU by visit, including but not limited to doctor/home/emergency visits, hospitalizations, paid assistance, and missed work
- Time to first flare; flare-free status at Weeks 24, 52, and 104; and annualized flare rate, will be analyzed separately, each assessed with flare defined as:
  - BILAG A Severe flare
  - BILAG A or 2B Moderate to Severe flare
  - SLEDAI Flare Index (SFI) Severe flare.

### 8.4 Analysis Sets

The statistical analyses described in this protocol will be based on the analysis sets defined below:

#### **Enrolled**

The Enrolled analysis set will include all subjects who sign the ICF.

### **Intent-to-Treat**

The Intent-to-Treat (ITT) Analysis Set will include all randomized subjects. Subjects will be analyzed according to randomized treatment.

### **Modified ITT**

The modified Intent-to-Treat (mITT) Analysis Set will include all randomized subjects who have received at least one dose of IMP (M2951 or placebo), and have at least one Baseline and one post-Baseline disease assessment. Subjects will be analyzed according to randomized treatment.

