## 8 Statistics

### 8.1 Sample Size

A sample size of 103 evaluable subjects per group provides 80% power at the  $\alpha = 0.025$  one-sided significance level to detect

- an absolute improvement of 20% in Week 52 SRI-4 response proportion for M2951-treated subjects relative to placebo-exposed subjects, among subjects with SLEDAI-2K total score  $\geq 6$  at Screening, assuming a placebo response proportion of 40%,

or

- an absolute improvement of 25% in Week 52 SRI-6 response proportion for M2951-treated subjects relative to placebo-exposed subjects, among subjects with SLEDAI-2K total score  $\geq 10$  at Screening (i.e., HDA), assuming a placebo response proportion of 30%,

assuming that each co-primary endpoint is tested via a chi-squared test of the odds ratio (OR) for treatment effect at the 0.0125 one-sided level, and assuming that approximately 50% of randomized subjects are in the HDA group. If the absolute improvement in Week 52 SRI-6 response proportion in HDA subjects is only 20%, the power is 76%. Approximately 108 subjects will be randomized per treatment group to protect against a loss of information due to drop-out (for reasons other than efficacy/safety) of 5% over 52 weeks. Given the randomization ratio 1:1:1:1, the total sample size required for the primary analysis is planned to be 432 subjects.

Approximately 432 subjects will enter the main study. Assuming an 80% rate of continuation to LTE, approximately 346 subjects are expected to enter the LTE Period.

The Japan cohort size was determined to provide a reliable evaluation of consistency in the Week 52 SRI-4 response proportion between the non-Japan and Japan regions. Assuming that:

- (i) the Week 52 SRI-4 response proportion in the placebo group is 0.40 for both the non-Japan and Japan regions,
- (ii) the Week 52 SRI-4 response proportion due to each of the 3 M2951 dose groups is 0.60 for both regions, so that the true underlying effect size is 0.20 for both regions,
- (iii) a total evaluable sample size of 412 (i.e., 309:103 randomization for M2951: placebo) is involved in analysis of the two regions,

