For SRI-4 or SRI-6 response at Week 52 (Week 24), a subject experiencing flare or CS dose increase during Weeks 41 to 52 (Weeks 17 to 24), or a subject with a missing response at Week 52 (Week 24), will be considered a non-responder. Four sensitivity analyses of the primary analysis are planned: (1) non-responder imputation for subjects discontinuing treatment for reasons due to efficacy/safety, with available observations used (in MMRM or multiple imputation) for subjects discontinuing treatment for reasons unrelated to efficacy/safety or completing treatment with missing response at Week 52, (2) unadjusted analysis, (3) completer analysis, and (4) per-protocol analysis (i.e., excluding subjects with clinically important protocol violations). Additional procedures for handling missing, unused, or spurious data, and sensitivity analyses exploring the impact of missing data will be described in the IAP.

The IAP will provide definitions of Baseline measurement as needed for change from Baseline endpoints.

Treatment compliance will be assessed in terms of the percentage of the actual doses taken relative to the number of scheduled doses and summarized by descriptive statistics.

All subjects will be included in individual subject data listings.

Any changes in the data analysis methods described in the protocol will require an amendment only if the change affects a principal feature of the protocol. Any other changes to the planned data analysis that does not require a protocol amendment will be described in the IAP and the CSR.

CCI

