## 8.5.2 Analysis of Primary Endpoints

The primary analysis of SRI-4 response at Week 52 among all subjects in the primary analysis cohort, and SRI-6 response at Week 52 among HDA subjects in the primary analysis cohort, will be an estimate of OR, together with associated two-sided 95% CI and p-value (testing null hypothesis  $H_0: OR = 1.0$ ), comparing each M2951 dose group to placebo, based on a logistic model for the odds of a given SRI response in the appropriate population, with M2951 dose group or placebo group as a factor and adjustment for covariates based on randomization strata. Additional covariates may be included in the model as specified in the IAP. In the primary analysis of SRI-4 or SRI-6 response at Week 52, a subject experiencing flare or CS dose increase during Weeks 41 to 52, or a subject with a missing response at Week 52, will be considered a non-responder.

The primary analysis of the co-primary efficacy endpoints will be based on the mITT analysis set, with supportive analyses based on the ITT and PP analysis sets, if the size of these analysis sets differ substantially ( $> 10\%$ ) from the size of the mITT analysis set.

The Family-Wise type 1 error rate (FWER) due to the co-primary endpoints and multiple M2951 dose group comparisons versus placebo will be controlled at the two-sided  $\alpha = 0.05$  level via a tree

gatekeeping procedure. The four hypotheses associated with the comparisons involving the co-primary endpoints and the two highest dose groups will form the first family of hypotheses in the tree. This family will be tested via the truncated Hochberg procedure, with truncation fraction pre-specified in the IAP. The multiple-testing procedure for the remainder of the tree, including the hypotheses associated with the comparisons involving the co-primary endpoints and the lowest dose group will be specified in the IAP.

A test for monotonic dose-response relationship, between ordered M2951 dose and SRI-4 response OR relative to placebo, will be performed as a supportive analysis. Similarly, a test for monotonic dose-response relationship, between ordered M2951 dose and SRI-6 response OR relative to placebo, will be performed as a supportive analysis in the HDA subgroup.

Descriptive statistics for SRI-4 response, and for SRI-6 response in the HDA subgroup, will be provided for each treatment group by time point.

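### The primary mITT set drops dosed subjects without a post-Baseline assessment whom the endpoint rules already count as non-responders, and the size-based ITT trigger would not show an arm imbalance

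*Protocol*

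**What the plan says.** - **Sets (Section 8.4).** "The Intent-to-Treat (ITT) Analysis Set will include all randomized subjects". The mITT set requires at least one dose and, in addition, that subjects "have at least one Baseline and one post-Baseline disease assessment". What counts as a disease assessment is not defined.
- **Primary analysis (Section 8.5.2).** The co-primary analysis "will be based on the mITT analysis set, with supportive analyses based on the ITT and PP analysis sets", but those supportive analyses are done only "if the size of these analysis sets differ substantially", which the section sets at more than 10%. It does not say whether the 10% applies overall, per arm or within the high disease activity (HDA) subgroup, nor which set is the denominator.
- **Missing outcomes (Section 8.5.2).** In the primary analysis "a subject with a missing response at Week 52, will be considered a non-responder".
- **Endpoint (Section 8.3.1).** SRI response requires, as its fourth condition, that the investigational product was not discontinued.
- **Sensitivity analyses (Section 8.5.1).** "Four sensitivity analyses of the primary analysis are planned": a hybrid of non-responder imputation with MMRM or multiple imputation, an unadjusted analysis, a completer analysis and a per-protocol analysis. None is on the ITT set. The per-protocol analysis appears here without condition, whereas Section 8.5.2 makes it depend on the 10% rule.

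**The concern.** Having a post-Baseline assessment is decided after randomization, so treatment can influence it. A dosed subject who leaves before any assessment is a failure on both the discontinuation rule and the missing-data rule, yet the set definition removes that subject from numerator and denominator. If one arm loses more such subjects than another, its response proportion rises relative to the all-treated result. In a dose-ranging trial, early tolerability may differ between doses.

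The planned check does not address this risk. Bias of this kind is driven mainly by imbalance between arms, while the trigger looks at size. A marked imbalance in one arm can leave the overall difference in set sizes far below 10%, and no ITT result would then be called for.

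**Working it through.** **The plan's own figure.** Section 8.1 states "A sample size of 103 evaluable subjects per group provides 80% power at the" one-sided 0.025 level, with each endpoint tested at 0.0125. At one-sided 0.0125, SRI-4 (40% vs 60%, n = 103) has 74.0% power and SRI-6 in HDA subjects (30% vs 55%, n = 51.5) has 63.1%. Read as success on at least one endpoint, with correlation 0.7 between the test statistics, this gives 80.5%, and 76.3% when the HDA effect is 20 points; the protocol states 80% and 76%. Drop-out inflation is 103/0.95 = 108.4, consistent with about 108 per group and 4 × 108 = 432. The sample size is not at fault. The protocol gives no expected number of subjects without a post-Baseline assessment, so every exclusion count below is an assumption.

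**How much the trigger tolerates (432 randomized).**
- Relative to mITT: 39/393 = 9.9%, 40/392 = 10.2%, so up to 39 exclusions.
- Relative to ITT: 43/432 = 9.95%, 44/432 = 10.2%, so up to 43.
- Ten exclusions in a single arm: 10/108 = 9.3% of that arm, but 10/432 = 2.3% overall.

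**Effect on the difference.** Let the response among assessed subjects be 60% (active) and 40% (placebo), with e_A and e_P excluded from 108 per arm, all of them non-responders. The mITT difference is always 20.0 points. On all treated subjects it is

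D = [0.6 × (108 − e_A) − 0.4 × (108 − e_P)] / 108

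| e_A, e_P | D | Points |
|---|---|---|
| 5, 2 | (61.8 − 42.4)/108 | 18.0 |
| 8, 2 | (60.0 − 42.4)/108 | 16.3 |
| 10, 2 | (58.8 − 42.4)/108 | 15.2 |
| 3, 3 | (63.0 − 42.0)/108 | 19.4 |
| 2, 5 | (63.6 − 41.2)/108 | 20.7 |

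The last row shows that the direction depends on which arm loses more.

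**Effect on a borderline result.** These are unadjusted pooled z-tests with one-sided p. Take 57/108 vs 43/108 responders on all randomized subjects.
- No exclusions: 13.0 points, p = 0.028.
- 5 active and 0 placebo non-responders removed: 57/103 − 43/108 = 15.5 points, p = 0.012.
- 3 removed from each arm: 57/105 − 43/105 = 13.3 points, p = 0.027.

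**Effect on type I error.** This is a simulation of one comparison with 40% response in both arms and nominal one-sided 0.0125. All excluded subjects are non-responders.

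| Excluded active, placebo | Rejection rate |
|---|---|
| 0, 0 | 0.012 |
| 2, 0 | 0.016 |
| 5, 0 | 0.030 |
| 10, 0 | 0.055 |
| 5, 5 | 0.015 |

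The 0.0125 level is the one used in Sections 8.1 and 8.5.1. Under the truncated Hochberg procedure the level applied to a given comparison may differ, so these figures show sensitivity rather than the trial's actual error rate.

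**The case against.** The strongest reply is that few subjects will be excluded. Under Sections 5.5.2 and 7.1.2.1, anyone who stops treatment is to attend an Early Withdrawal visit within five days and then a Safety Follow-Up visit. Table 1 schedules SLEDAI-2K, BILAG 2004, PGA and CLASI at both, and attending either one meets the mITT condition. The first scheduled post-dose laboratory tests are at Week 2, when CLASI is also assessed. Section 5.1 groups CLASI with the disease activity measures, so a subject stopped on a Week 2 laboratory result may already qualify. This stands, and it limits the likely size.

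It does not remove the point. Section 5.5.1 lets subjects withdraw at any time without a reason, so exit visits are not assured. The Amendment 14 change list gives, as a rationale, drop-out unrelated to efficacy or safety that was higher than anticipated, though it does not say that this drop-out precedes an assessment.

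Three stronger readings are tempting, and the documents support none of them.
- A reader might infer that the primary result will be inflated by several points in favour of a poorly tolerated dose. That needs an excess of exclusions in the active arm, for which the protocol gives no evidence.
- A reader might take 39 to 43 exclusions as likely. That is the ceiling of the trigger, not a forecast.
- A reader might call Sections 8.4 and 8.5.2 contradictory. They can operate in sequence: the set is formed first and missing outcomes are imputed within it. The fault is a needless exclusion, not an impossible instruction.

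Section 8.5.1 also leaves further missing-data sensitivity analyses to the analysis plan, so an ITT analysis may be added there. Only the absence of ITT from the four listed analyses and the conditional wording of Section 8.5.2 can be criticized here.

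**Conclusion.** The point holds as a design weakness that should be corrected, with a probably small effect. The post-Baseline condition removes dosed subjects whose outcome is already fixed as non-response, so it gains nothing and opens a route to arm-dependent selection. If exclusions are few or balanced, the primary result barely moves (3 vs 3: 13.3 against 13.0 points). If they are unbalanced, even a handful matters: 18.0 instead of 20.0 points at 5 vs 2, or a one-sided p of 0.012 instead of 0.028 at 5 vs 0. These sizes rest on assumed counts and on treating every excluded subject as a non-responder, which the protocol's own rules imply for dosed early leavers.

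The 10% trigger is a poor safeguard whatever the counts turn out to be, because it responds to size and its denominator and level are unspecified. The per-protocol mismatch between Sections 8.5.1 and 8.5.2 is real, but it is a separate wording matter.

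**What to change.** 1. In Section 8.4, define the primary set for the co-primary analyses as all randomized subjects who took at least one dose (or the full ITT set), analysed as randomized, with no post-Baseline-assessment condition.
2. Keep non-responder imputation for missing Week 52 responses as in Section 8.5.2.
3. In Section 8.5.2, delete the 10% trigger and report the ITT analysis unconditionally.
4. Reconcile Sections 8.5.1 and 8.5.2 on whether the per-protocol analysis is always done.

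The cost is a change of wording, with no new visits or data. Response rates may come out slightly lower, because early leavers stay in the denominator.

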### **Per-Protocol**

The Per-Protocol (PP) Analysis Set will include all randomized and treated subjects who do not have any clinically important protocol deviations. Details of the criteria for exclusion from the PP analysis set will be provided in the IAP, including exclusion of subjects who take prohibited medications. Subjects will be analyzed according to randomized treatment.

### **Safety**

The Safety Analysis Set will include all randomized subjects who receive at least one dose of IMP, and will be used for the evaluation of safety endpoints. Subjects will be analyzed according to the actual treatment they receive.

CCI

CCI

CCI

### **Long Term Extension Analysis Set**

The LTE Analysis Set consists of all subjects who receive at least one dose of M2951 during the LTE.

CCI

### 8.4.1 Subgroups

Descriptive analyses of efficacy will be performed for the following subgroups:

- Race (Black, non-Black) (see Section 6.3 for definitions of Race used in this study)
- Ethnicity (Japanese, non-Japanese) (Hispanic/Latino, non-Hispanic/Latino)
- Severity of disease at Screening (severe, mild/moderate). Severe is defined as at least one BILAG A; mild/moderate is defined as at least one BILAG B and no BILAG A. Analyses of subgroups defined in terms of SLEDAI-2K total score at Screening ( $< 10$  versus  $\geq 10$ ) will also be performed.
- Serological activity status (positive versus negative). Serologically active is defined as positive anti-dsDNA and/or low complement levels.
- Age ( $< 65$ ,  $\geq 65$ ).
- Gender (male, female).
- Region (US and Western Europe, Japan, and RoW).
- Subjects on background therapy that includes mycophenolate versus subjects not taking mycophenolate.

